### 8.2.1 Severity Assessment

The severity of adverse events should be assessed by CTCAE v.5. If an event is not listed in CTCAE v.5 then the assessment of severity should follow the general guidelines listed in Table 3.

**Table 2: Severity assessment**

Grade	Severity Description
1	Mild event that generally does not require intervention.
2	Moderate event that may require intervention.

3	Severe event that requires intervention.
4	Life-threatening event that requires urgent intervention.
5	Death.

Events meeting grade 4 or 5 severity description should be reported promptly as SAEs unless otherwise indicated in Section 8.1.2.

### **8.2.2 Causality Assessment**

The Investigator should assess the causality or relationship of AEs and SAEs to study therapy. The Investigator should consider if there is evidence that the investigational product caused the event taking into consideration timing, organ system affected, type of event, and possible alternative etiologies. The relationship of the AE to study treatment will be reported as listed below. These categories will be defined as follows:

- Definitely related – a clinical event, including laboratory test abnormality, occurring in a plausible time relationship to drug administration, and which cannot be explained by concurrent disease or other drugs or chemicals. The response to the withdrawal of the drug (dechallenge) should be clinically plausible. The event must be definitive pharmacologically or phenomenologically, using a satisfactory rechallenge procedure if necessary.
- Probably related – a reasonable time sequence to the administration of the drug, unlikely to be attributed to concurrent disease or other drugs or chemicals, and which follows a clinically reasonable response on withdrawal (dechallenge). Rechallenge information is not required to fulfill this definition.
- Possibly related – a reasonable time sequence to administrations of the drug, but which could also be explained by concurrent disease or other drugs or chemicals. Information on drug withdrawal may be lacking or unclear.
- Unlikely related – a temporal relationship to drug administration which makes a causal relationship improbable, and in which other drugs, chemicals or underlying disease provide plausible explanations.
- Not related – there is no evidence of a causal relationship between the study drug and the event and in which other drugs, chemicals or underlying disease explain the event.

Adverse events reported as definitely, probably, and possible, related to study therapy will be reported as related. In cases when the Investigator is unsure of the causality of an AE, the event will be considered related to study therapy unless deemed otherwise by the DSMC.

### **8.2.3 Expectedness**

The Investigator will be responsible for determining whether or not an adverse event was expected or unexpected. Expected adverse events are those adverse events that are listed or characterized in the Package Insert (PI) or current Investigator Brochure (IB). Unexpected adverse events are those not listed in the PI or current IB or not identified. This includes

adverse events for which the specificity or severity is not consistent with the description in the PI or IB. For example, under this definition, hepatic necrosis would be unexpected if the PI or IB only referred to elevated hepatic enzymes or hepatitis.

#### **8.2.4 Action Taken and Outcome**

Start and stop dates will be required for all adverse events and serious adverse events. The action taken in response to the event should also be recorded in the subject's research chart and corresponding eCRF. Event action terms include none, medication administered, non-drug therapy administered, surgery, hospitalization, or other with the option to specify. If a new medication is added the medication should also be added to the concomitant medications log.

All adverse events should be followed until stabilization or resolution. Event outcomes may be classified as resolved, resolved with sequelae, ongoing, or death.

#### **8.2.5 Reporting Serious Adverse Events**

All serious adverse events should be reported as soon as possible but no later than one business day after the Investigator becomes aware. All SAEs must be reported via the HCI CTMS (OnCore) and submitted to [[contact]](mailto:[contact]). The HCI Clinical Site Monitor will in turn, submit the report to the Medical Monitor. The RCO will summarize and present all reported SAEs according to the Data and Safety Monitoring Plan at the monthly DSMC meeting.

At a minimum, initial SAE reports must include a description of the event, assessment of event causality, event grade, and the expectedness of the event. Although the Investigator may not know all the information at the time of the event, the available information should be reported. An SAE follow-up may be submitted at a later date once more information is known. It is required that follow-up reports be submitted until the SAE is resolved.

#### **Follow-Up Information**

It is recommended that follow-up reports be submitted as new information becomes available, however, a follow-up report should be submitted within 3 days of knowledge of event resolution. Follow-up information will be added to the SAE in OnCore and submitted to the DSMC via RCO.

#### **8.2.6 FDA Notifications**

This study will not hold an IND.

#### **8.2.7 IRB Notification**

The University of Utah IRB requires any unanticipated problems that may increase the risk to research participants be promptly reported. All study-therapy related, unexpected adverse events whose nature, severity, or frequency is not consistent with either:

- The unknown or foreseeable risk of adverse events that are described in the protocol related-documents, such as the IRB-approved research protocol, applicable investigator brochure, the current IRB-approved informed consent document, and/or other relevant sources of information, such as product labeling and package inserts; or

- The expected natural progression of any underlying disease or condition of the subject(s) experiencing the adverse event.

Adverse events meeting this criterion must be promptly reported to the IRB within 10 business days of awareness.

### **8.3 Special Situations**

#### **8.3.1 Pregnancy or Breastfeeding**

Although pregnancy is not considered an adverse event, any exposure to the investigational products during pregnancy or breastfeeding must be reported promptly. Exposure may occur by a woman actively receiving study therapy or the partner of a male subject actively receiving study therapy becomes pregnant. Any possible pregnancy or breastfeeding exposure during study therapy and up to 30 days after the last dose of study therapy or up to the start of subsequent anticancer therapy (whichever happens first) must be reported within one business day of awareness regardless of the occurrence of an SAE. Should a woman on study therapy become pregnant, she should immediately discontinue study treatment.

Women exposed to IP during pregnancy or while breastfeeding will be followed for pregnancy outcome and neonate health. Pregnancy outcomes may meet criteria as an SAE if ectopic pregnancy, spontaneous abortion, intrauterine fetal demise, neonatal death, or congenital anomaly occurs. Congenital anomalies that occur in a live-born baby, a terminated fetus, an intrauterine fetal demise, or a neonatal death should be reported as an SAE. Any neonatal deaths that occur up to 30 days after birth or breastfeeding exposure should be reported as an SAE. Further follow-up on birth outcomes and neonate health will be handled on a case-by-case base.

#### **8.3.2 Hy's Law Cases**

It is important to identify possible cases of Drug-Induced Liver Injury (DILI) early. Total bilirubin, AST, and ALT should be regularly monitored for elevations indicative of liver damage. Subjects who experience a transaminase elevation above three times the ULN should be monitored frequently to determine if the elevation is transient. Transient elevations are an indication of adaption and these subjects may be identified as “adaptors.” However, should a transaminase elevation be followed by total bilirubin (TBili) increase, a DILI could be occurring. Any laboratory abnormalities meeting the following criteria should be reported within 24 hours of awareness:

- AST or ALT elevation  $> 3 \times$  ULN; and
- Total bilirubin  $> 2 \times$  ULN; and
- Absence of cholestasis; and
- No alternative explanation for the elevations (e.g., impaired glucuronidation capacity caused by genetic [Gilbert syndrome]; viral hepatitis A, B, or C, preexisting or acute liver disease; or another drug capable of causing the observed injury).

Investigators should conduct reasonable investigations to rule out other possible etiologies. Investigators should take into consideration the subject's use of ethanol, acetaminophen,

recreational drugs, herbal supplements, and medical history. A potential Hy's Law case will not be considered a confirmed case until all results and considerations have excluded alternative etiologies.

Possible cases of DILI will be promptly reported to the FDA prior to full work up to rule out other etiologies. Reporting should be completed on a MedWatch 3500A form and should include all available information, including the likelihood that the drug caused the event. Subjects should be closely followed until the resolution of the event.

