### 5.1 Inclusion Criteria

1.  Subject aged  $\geq$  18 years.
2.  Subjects with non-operable GI cancers requiring multi-modal treatment (e.g. surgery +/- chemo +/-radiation) and have a high likelihood of recurrence and/or treatment failure in the opinion of the treating investigator.
3.  Screen positivity for existential distress on the EDS, defined as scoring  $\geq$  3 on any of the 10 component domains, or a total score  $\geq$  6
4.  ECOG Performance Status  $\leq$  2.
5.  Adequate hepatic function as defined as:
  - Total Bilirubin  $\leq$  1.5x institutional upper limit of normal (ULN) unless elevated bilirubin is related to Gilbert's Syndrome
  - AST(SGOT)/ALT(SGPT)  $\leq$  3  $\times$  institutional ULN
    - Subjects with liver metastases will be allowed to enroll with AST and ALT levels  $\leq$  5  $\times$  ULN.
6.  For subjects of childbearing potential: Negative pregnancy test or evidence of post-menopausal status. The post-menopausal status will be defined as having been amenorrheic for 12 months without an alternative medical cause. The following age-specific requirements apply:
  - Subjects  $<$  50 years of age:
    - Amenorrheic for  $\geq$  12 months following cessation of exogenous hormonal treatments; and
    - Luteinizing hormone and follicle-stimulating hormone levels in the post-menopausal range for the institution; or
    - Underwent surgical sterilization (bilateral oophorectomy or hysterectomy).
  - Subjects  $\geq$  50 years of age:
    - Amenorrheic for 12 months or more following cessation of all exogenous hormonal treatments; or
    - Had radiation-induced menopause with last menses  $>1$  year ago; or

- Had chemotherapy-induced menopause with last menses >1 year ago; or
- Underwent surgical sterilization (bilateral oophorectomy, bilateral salpingectomy, or hysterectomy).

7.  Subjects of childbearing potential and subjects with a sexual partner of childbearing potential must agree to use a highly effective method of contraception as described in Section 5.3.1.

8.  Subjects with a sexual partner of childbearing potential must agree to use a condom during intercourse for 24 hours post- ketamine dose.

9.  Agree to refrain from using any psychoactive drugs, including alcoholic beverages, ondansetron, cannabis, and non-routine PRN medications within 24 hours of each ketamine administration. Exceptions include daily use of caffeine, nicotine, and opioid pain medication (see Section 6.5.1).

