10.  Able to provide informed consent and willing to sign an approved consent form that conforms to federal and institutional guidelines.

11.  Agree that for one week preceding the ketamine session, he/she will refrain from taking any nonprescription medication, nutritional supplement, or herbal supplement except when approved by the research team. Exceptions will be evaluated by the research team and will include acetaminophen, non-steroidal anti-inflammatory drugs, and common doses of vitamins and minerals.

12.  Agree not to use nicotine for at least 2 hours before the ketamine administration or for the duration of the ketamine session.

13.  Agree to consume approximately the same amount of caffeine-containing beverage (e.g., coffee, tea) that he/she consumes on a usual morning, before arriving at the research unit on the morning of the ketamine session. If the subject does not routinely consume caffeinated beverages, he or she must agree not to do so on the day of ketamine administration.

14.  Subjects requiring opioid use for pain are on a stable pain management regimen or do not experience clinically significant sedation during opioid use.

- Note: Long-acting opioid medications (e.g., oxycodone sustained-release, morphine sustained release) will be allowed if the last dose occurred at least 6 hours before ketamine administration; such medication will not be taken again until at least 6 hours after ketamine administration.

15.  Fluent in English.

16.  Reading literacy and comprehension sufficient for understanding the consent form and study questionnaires, as evaluated by study staff obtaining consent.

17.  Have a support person who is be able to escort the subject home from the ketamine dosing sessions.

- Note: The use of ride services will not be permitted (e.g., Uber, Lift, taxi, etc.)

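### Section 8.3.2 makes the absence of another explanation a condition of the 24-hour Hy's Law report, although the same section uses exclusion of other causes to confirm a case

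*Combined protocol and SAP*

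**What the plan says.** Section 8.3.2 sets a 24-hour clock for laboratory abnormalities that satisfy four bullets, each joined to the next by 'and'. Three describe the finding itself: AST or ALT above 3 x ULN, total bilirubin above 2 x ULN, and no cholestasis. The fourth is "No alternative explanation for the elevations". Its examples are Gilbert syndrome, then "viral hepatitis A, B, or C, preexisting or acute liver disease; or another drug capable of causing the observed injury". The section does not name the recipient of this report.

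Three further statements follow in the same section. Investigators are to look for other causes, taking account of the subject's "use of ethanol, acetaminophen" and other exposures. A potential case "will not be considered a confirmed case until all results and considerations have excluded alternative etiologies". And "Possible cases of DILI will be promptly reported to the FDA prior to full work up to rule out other etiologies".

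Other sections bear on how often a rival cause might be present. In section 5.1, criterion 11 restricts non-prescription medicines before a session, but "Exceptions will be evaluated by the research team and will include acetaminophen". Criterion 2 admits "Subjects with non-operable GI cancers requiring multi-modal treatment", with chemotherapy among the examples. Criterion 5 lets subjects with liver metastases enter with AST and ALT up to 5 x ULN. On monitoring, section 8.3.2 states that "Total bilirubin, AST, and ALT should be regularly monitored for elevations indicative of liver damage", while the Schedule of Events (section 1.4) marks the metabolic panel at screening only. Section 7.2.3 also allows samples when clinically indicated.

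**The concern.** An early-warning report is meant to go out while the cause is still open. Here the early report is conditional on a judgement about cause, and the section elsewhere treats that judgement as the outcome of the work-up. The subject most likely to fall through is one with the full laboratory pattern and a plausible but unproven competitor, such as a concomitant drug. The bullet's own examples make that exclusion easy to apply.

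At stake is the speed of one safety notification. The section opens by stressing early identification of possible drug-induced liver injury, and section 8.4 classifies the trial as high risk, so the rule should match that aim. Nothing here touches sample size, an error rate or an endpoint.

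**Working it through.** No formula applies. The check is to write the rule out and see which subjects it reaches.

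**The rule.** Let A be AST or ALT above 3 x ULN, B total bilirubin above 2 x ULN, C absence of cholestasis, and D no alternative explanation. Because the bullets are joined by 'and', the 24-hour report is due only when A, B, C and D all hold. A potential case is confirmed when E holds: every alternative has been excluded once all results are in.

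**Two readings of D.**

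1. *Strict: D is the same as E.* The trigger then already contains the confirmation test. Any case that met it would be confirmed on arrival, and the sentence separating potential from confirmed cases would have nothing to do.
2. *Charitable: D means none apparent so far.* This fits the order of the section (awareness, investigation, confirmation) and is probably what was intended, although the text does not say so.

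**Who is reached.** Take subjects for whom A, B and C all hold.

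| Subject's situation at awareness | Strict reading | Charitable reading | Trigger on A, B, C only |
|---|---|---|---|
| No rival cause apparent, work-up incomplete | no | yes | yes |
| Rival cause plausible, not established | no | no | yes |
| Rival cause established | no | no | yes |

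The middle row is the point. It stays outside the 24-hour report on either reading, yet on ordinary language it is a possible case that the FDA sentence would cover before work-up ends. The section gives no separate laboratory definition of a possible case.

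**Whether another section closes the gap.** Four provisions come close.

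- The FDA sentence in 8.3.2 covers possible cases, but says only promptly and sets no number of hours.
- Section 8.1.1 lets an abnormal result be recorded as an adverse event, for example if it needs further testing. It also says disease progression is not reported as an adverse event, so a rise put down to hepatic progression might not take this route.
- Section 8.2.2 counts an event of unsure causality as related unless the DSMC decides otherwise. That concerns adverse-event attribution and does not alter the four bullets.
- Section 8.2.5 gives one business day for a serious adverse event. Reaching it may depend on the judgement of medical significance described in 8.1.2.

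None of them changes the 24-hour list.

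**How often the rule could be reached.** The Schedule of Events has 9 visit columns: screening, preparatory, three ketamine sessions, integration, and days 14, 30 and 90. The metabolic panel is marked in 1 of them, screening, and so in 0 of the 8 later columns. Planned exposure is 12 subjects x 3 doses = 36 doses. The documents give no rate of liver injury, so neither a probability nor a count of missed reports can be derived.

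**The case against.** The strongest reply is that the section reads coherently from top to bottom. The clock starts at awareness, so the fourth bullet can be judged only on what is known then. Confirmation uses a stricter standard after all results are in. These are different thresholds, and at most a word such as 'apparent' is missing. Much of this stands: the text is not a flat contradiction, and the charitable reading is the better one. It does not rescue the rule, because a subject with an apparent but unproven rival cause is still left out.

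The second reply is that the harm is largely covered and the clause rarely reachable. That also stands, and it sets the weight of the point. What remains is a gap in the 24-hour report, whose recipient is not stated.

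The third reply is that dropping the fourth bullet will pull in subjects with liver metastases. They may meet the transaminase criterion at entry, and their bilirubin may rise through evident progression. This is a real cost. A Hy's Law notification is not the same thing as recording progression as an adverse event, but some such notifications will later be attributed to the cancer.

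A reader might infer that these cases would go unreported altogether. The documents do not support that, since possible cases still go to the FDA before work-up is complete. A reader might also infer that nearly every subject has a rival cause on board. Criterion 2 speaks of cancers requiring multi-modal treatment, which is not the same as subjects receiving chemotherapy during the study. Acetaminophen is a permitted exception, not a required one. And the text does not say that liver metastases count as pre-existing liver disease.

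**Conclusion.** The point holds as a cheap improvement. As written, a subject with AST or ALT above 3 x ULN, bilirubin above 2 x ULN and no cholestasis, but with a plausible rival cause, is not covered by the 24-hour report. That runs against the section's stress on early identification and its willingness to report possible cases before the cause is settled.

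The weight is low. No liver panel is scheduled after screening, so only clinically indicated or routine-care results can set the trigger off, and the study plans 12 subjects. No endpoint or analysis is affected.

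The conclusion rests on reading the four bullets as jointly required, which is what their connectors say. It does not depend on choosing the strict reading of the fourth bullet. Whether the instruction to monitor liver tests regularly needs a panel after screening is a separate question that this point does not settle.

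**What to change.** Keep the first three bullets as the trigger and move the fourth, with its examples, to the sentence on confirmed cases. For example:

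> AST or ALT above 3 x ULN with total bilirubin above 2 x ULN and absence of cholestasis is a potential Hy's Law case. It is reported within 24 hours of the site learning of it, whether or not another cause is suspected. The case is confirmed only when alternative explanations [existing examples] have been ruled out.

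Three things should stay as they are. Do not limit the trigger to post-dose results, because the present text covers any laboratory abnormality. Do not add a default for unclear cholestasis, which would be a second rule change. Leave the FDA sentence alone, so that route is not narrowed by a laboratory threshold.

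The cost is moving one bullet and rewording the text around it at the next amendment, with no new tests. The downside is some early reports later attributed to the cancer (including hepatic progression in subjects with liver metastases), to its treatment or to Gilbert's Syndrome. Their number cannot be estimated from the documents, but enrolment of 12 limits how many subjects could contribute.

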#### **8.4 Data Safety Monitoring Committee**

A Data Safety Monitoring Committee (DSMC) at HCI is charged with ensuring the risk/benefit balance for subjects undergoing study therapy. The purpose of the DSMC is to ensure subject safety and make recommendations for study conduct to ensure subject safety and data integrity. The DSMC is chaired by a medical oncologist and may include, but is not limited to, representatives from medical oncology, oncological sciences, biostatistics, and pharmacy.

The roles and responsibilities of the DSMC are described in the NCI-approved Data and Safety Monitoring (DSM) plan. The activities of the committee include reviewing adverse events (including SAEs), deviations, important medical events, and approving cohort/dose escalations. Amendments that increase risk, increase treatment exposure, or impact study objectives will also be reviewed by the DSMC. If the DSMC and/or the PI have concerns about unexpected safety issues or AE trends, the study may be stopped and an unplanned safety data analysis may be conducted. Enrollment will not resume until the issues are resolved. The DSMC also reviews and approves audit reports generated by the Research Compliance Office.

All trials will be assigned and an oncologist member of the DSMC to serve as a medical monitor. In rare cases, an external medical monitor may be assigned. The Medical Monitor will be notified of all serious adverse events (SAEs). Specific notifications will also be issued when a dose-limiting toxicity is encountered and when the RP2D is defined. Approval from the Medical Monitor is required for all dose escalations. All serious adverse events (SAEs) occurring in subjects treated at HCI or its affiliates will also be reviewed by the full DSMC monthly.

Each trial is assigned a research compliance officer who will be responsible for monitoring the trial and reporting to the DSMC. The assessed risk level of the trial will determine the frequency with which monitoring occurs. The Research Compliance Officer monitor will review the study status and summarize enrollment, toxicities, SAEs, dose-escalation, statistical endpoints (e.g., stopping rules), deviations, and any other pertinent information for the full DSMC membership at the regularly scheduled meetings.

Audits will be conducted for all trials one year after enrollment begins and annually thereafter. Audits may be conducted more frequently as requested by the DSMC, Institutional Review Board (IRB), Protocol Review and Monitoring Committee (PRMC), Research Compliance Office management, or the Principal Investigator.

DSMC oversight will be tailored to the assessed risk level of the trial. Trials are categorized amongst three risk levels: high, moderate, and low.

This trial has been classified as high risk and therefore will be monitored by RCO and reviewed by DSMC after the first subject is enrolled and then quarterly thereafter.

